1. BACKGROUND AND SIGNIFICANCE

COVID-19 causes severe respiratory disease, disability, and death among older adults.¹ Vaccination is an essential step in the prevention of disease spread and mitigation of disease severity to promote healthy aging. Despite this, about 1 in 4 Americans report hesitation about receiving the COVID vaccine, even when free and reported as safe by scientists.² Moreover, hesitancy is higher among Black and Hispanic populations, which, if not directly addressed, could result in ongoing disparities in COVID infections and deaths.^{3,4} Early efforts to vaccinate Americans has shown a lot of early demand, but racial disparities in vaccination rates are already emerging,⁵ and once the initial interest from vaccine eager individuals has passed, interventions to engage more hesitant or resistant individuals will be needed to maximally protect the population from COVID-19.⁶

Patient outreach strategies for other vaccines have had modest success.⁷⁻⁹ Most of these approaches have focused on abstract concepts of *why* patients should receive a vaccine. However, messages that describe *how* to do something may be more effective at inducing behaviors that are psychologically near (e.g., imminent, personal), like scheduling a vaccination appointment for yourself within a week.

According to Construal Level Theory, emphasizing “why” elicits more abstract thinking, or high-level construals, and can induce an emotional mindset, which could challenge an individual’s sense of identity, autonomy, or political preferences. Conversely, emphasizing “how” is more cognitive and evokes concrete thinking, or low-level construals, and encourages a planning or implementation mindset.^{10,11} Low-level construals (“how” messages) have been shown to increase intention to or uptake of several health behaviors including dietary changes,¹² use of relaxation techniques,¹³ blood donation,¹⁴ and completion of biometric screening and health surveys.¹⁵ Though prior studies of vaccine acceptance have not explicitly applied Construal Level Theory, aspects of interventions that elicit low-level construals have been successful compared to other techniques. For example, straightforward messages stating that a dose of the flu vaccine was “reserved” for the patient at their upcoming appointment (low-level construal) were more effective than messages about protecting loved ones (high-level construals).¹⁶ Similarly, information on where and when to receive the flu shot outperformed gain- or loss-framed reminder messages,⁸ and a map of flu vaccine locations was more effective than a loss-framed message or an entry to win a \$100 gift card.¹⁷

Because of the political and emotional valence of the COVID-19 vaccine, “how” messaging to elicit concrete thinking may be particularly important. Direct comparison of “how” vs “why” messages has not been tested for vaccines, and it has never been tested for COVID-19. Moreover, COVID vaccine hesitancy differs by age, gender, and race,^{4,6} and demographic groups may respond differently to messages. Tailoring a message to a specific group with higher rates of vaccine hesitancy could help reduce health disparities.

Thus, in this study we propose a pilot randomized trial to test the effects of “how” vs “why” framing on COVID-19 booster vaccination rates using electronically delivered communication (e.g., patient portal messages delivered through the electronic health record [EHR]), followed by analyses to identify patient characteristics that might predict intervention responsiveness to allow for further tailored communication after the completion of the trial.

2. SPECIFIC AIMS

The main aims are to 1) test the effect of “how” vs “why” framed messages on the rates of COVID-19 booster vaccination and 2) assess association of clinical and demographic characteristics with intervention responsiveness.

The objectives and endpoints for this project are summarized below.

OBJECTIVES	ENDPOINTS	JUSTIFICATION FOR ENDPOINTS
Aim 1		
To test the effect of “how” vs “why” framed messages on the rates of COVID-19 vaccination	Primary : the rate of booster vaccination at the targeted visit Secondary : the rate of receipt of a COVID booster vaccine within 6 weeks of the targeted visit	These outcomes are directly related to the interventions, are clinically meaningful, and are measurable using routinely collected data in the Mass General Brigham COVID-19 Vaccine Registry and the Research Patient Data Registry (RPDR) and/or Epic Enterprise Data Warehouse (EDW). We plan to use RPDR for variable collection as long as all the variables needed are available in the RPDR. If a variable is not available in the RPDR then we will supplement with use of the EDW for those variables.
Aim 2		
To assess association of clinical and demographic characteristics with intervention responsiveness	A model to predict likelihood of response to each intervention based on patient characteristics	A model predicting intervention responsiveness could be used to tailor future interventions to specific patients

3. SUBJECT SELECTION

This study will include patient subjects for intervention and analysis. We will use the Mass General Brigham Research Patient Data Registry (RPDR) and/or Epic Enterprise Data Warehouse (EDW) to identify Mass General Brigham (MGB) patients age ≥ 18 who are eligible for the COVID booster vaccine, who have not received a dose as of the time of upcoming primary care clinic visit. We will then cross check that with the COVID-19 vaccine registry so that we can additionally exclude patients who may have received a vaccination that has not yet been entered into RPDR.

Patients will be excluded if they did not receive the full set of their primary COVID-19 series or had a severe allergic reaction to either dose of their primary series. All MGB patients who meet the criteria above will be eligible for the study. We plan to begin the study after the booster vaccine is widely available to individuals 18 years of age or older. Based on a recent survey data from the Kaiser Family Foundation, at least 45% of the fully-vaccinated population are at least somewhat skeptical about obtaining a booster vaccination.

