4.3 Treatment assignment and randomization

All eligible patients will be randomized to one of three arms: 1) “why” messaging, 2) “how” messaging, or 3) “standard of care (“usual care”). We plan to conduct stratified randomization based on the primary care clinic the patient attends to account for differences in patient populations between clinics. We will also use block-stratified randomization, in which the unit of randomization is the day of the week the study visit is on. This choice was made in response to the logistical difficulties randomizing at the patient level presented. Each weekday, eligible patients will be identified that have an upcoming visit 2-3 days from then. The day of the week of that visit will be randomized in a 1:1:1 ratio with a random number generator to one of three arms: 1) “why” messaging, 2) “how” messaging or 3) “standard of care” (“usual care”).

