5.2 Overall Design

We will use the Mass General Brigham COVID-19 Vaccine Registry and EHR information in the Research Patient Data Registry (RPDR) and/or Epic Enterprise Data Warehouse (EDW) to identify all patients age ≥ 18 with an upcoming primary care outpatient appointment who are eligible for the COVID booster vaccine. We plan to launch the study after the booster vaccine has become widely available to adults over age 18 and supply of vaccines at MGB is anticipated to be sufficient. All eligible patients will be randomized to one of three arms: 1) “why” messaging, 2) “how” messaging, or 3) standard of care (“usual care”). We will conduct stratified randomization based on the primary care clinic the patient attends and day of the week the upcoming visit is on.

The primary outcome will be the rate of booster vaccination at the targeted visit. Secondary outcome will be receipt of a booster vaccine within 6 weeks of the target visit at any location. After completion of the trial, we will utilize data from the RPDR and/or EDW to develop models that predict which patients are most likely to respond to each intervention using patient baseline characteristics, which in the future could allow for targeting of interventions to specific patients. We will use the Mass General Brigham COVID-19 Vaccine Registry and the RPDR/EDW for outcome measurement.

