5.2.1 Aim 1 Design

[figure not shown]
In Aim 1 of the study, we will conduct a 3-arm randomized controlled trial to compare the effectiveness of two interventions compared to usual care on COVID-19 vaccination uptake. We will include Mass General Brigham (MGB) patients age ≥ 18 with an upcoming primary care outpatient visit with a Mass General Hospital primary care provider who are eligible for the COVID booster vaccine and who have not received a dose. This approach has been approved by MGH primary care leadership. Patients will be excluded if they did not receive the full set of their primary COVID-19 series.

Patients will be randomized equally to one of three arms: 1) “why” messaging, 2) “how” messaging, or 3) standard of care (“usual care”). We plan to conduct stratified randomization based on the primary care clinic the patient attends to account for differences in patient populations between clinics and based on the day of the week the upcoming visit is on to minimize logistic difficulties in the intervention delivery. “Why” messages will focus on reasons to get the vaccine, including protecting self and loved ones or the idea of herd immunity. “How” messages will focus on the details of obtaining a vaccination at MGB, what to expect, and how to prepare for the visit. The messages will be sent through the EHR electronic patient portal for portal users. For patients whose primary language listed in the EHR is not English, they will be offered translated messages following standard MGB Gateway messaging practices. Gateway messages will first include a message translated in their primary language (Spanish, Portuguese, Arabic, Chinese, Russian, Haitian Creole or Bosnian) followed by an English version of the message. Consistent with recent studies for influenza vaccination and the approach approved by MGH primary care leadership, we will send a message to patients a few days in advance of their office visit.¹⁶ Based on current MGH practice (i.e., standard of care), patients in Arm 3 will not receive any additional message about their upcoming visit, beyond what they already receive by MGH. **Initial examples of these messages are attached.**

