5.6 End-of-study definition

The active interventions in Aim 1 are expected to last no more than 1 week. The study data collection of vaccination receipt will begin after the target primary care outpatient visit will conclude 1 month after the target visit is complete, as we anticipate some lag for complete vaccination information to be included in the MGB COVID-19 Vaccine Registry data source. Development of the prediction models will be done following Aim 1 data collection.

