6.5.2 Analysis of the secondary endpoints

Secondary outcomes will include in each arm the rate of receipt of COVID booster vaccine 6 weeks after the target primary care outpatient appointment. As in the primary analysis, we will use the MGB Research Patient Data Registry (RPDR) and/or Electronic Data Warehouse (EDW) for outcome measurement. We will use logistic regression to compare outcomes between each intervention arm versus usual care and against each other; in secondary analyses, we will additionally adjust for any imbalanced baseline characteristics.

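### Booster-free status is dated to the visit, 2-3 days after assignment and messaging, so the text permits a post-assignment exclusion that the message itself can cause; the 6-week window is also worded inconsistently

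*Combined protocol and SAP*

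**What the plan says.** Section 3 describes the patients to be included for both intervention and analysis. They are adults eligible for the booster "who have not received a dose as of the time of upcoming primary care clinic visit". It then adds a check against the vaccine registry, to "additionally exclude patients who may have received a vaccination that has not yet been entered into RPDR", and gives no date for that check.

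Section 4.3 sets the operational sequence: "Each weekday, eligible patients will be identified that have an upcoming visit 2-3 days from then". The day of that visit is then randomized. Section 5.2.1 adds that "we will send a message to patients a few days in advance of their office visit".

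The primary endpoint in Section 2 is "the rate of booster vaccination at the targeted visit". The secondary endpoint in Section 5.2 is "receipt of a booster vaccine within 6 weeks of the target visit at any location", and Section 2 also uses the *within* wording. Section 6.5.2 instead gives "the rate of receipt of COVID booster vaccine 6 weeks after the target primary care outpatient appointment". Section 5.6 states: "The study data collection of vaccination receipt will begin after the target primary care outpatient visit".

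No section says how a booster given between message and visit is treated, either for eligibility or for the two endpoints. Section 6.5 defines no analysis population.

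**The concern.** An eligibility condition should be settled before assignment, on information that the assigned arm cannot influence. Status at the time of a future visit cannot be known when the patient is identified. Applied as written, the condition is settled only after the message has gone out. A patient who reads it and is boosted elsewhere the next day would then leave the study. In usual care the same exclusion would remove only background boosters. The arms would no longer be compared as assigned, and a larger sample would not repair that.

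The undated registry check adds to the risk. Section 5.7 says the registry is refreshed weekly, so a check run after the next refresh could pick up doses given after the message and exclude those patients.

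The any-location secondary endpoint should capture these doses. It does so only if its window is open before the visit, and the wording in Section 6.5.2 leaves that in doubt.

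**Working it through.** **1. Order of events.** Identification and assignment come 2-3 days before the visit (Section 4.3). The message goes out in that interval (5.2.1). The date at which booster-free status is judged is the visit (Section 3, literal reading). The last step should come first.

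**2. The plan's own sample size.** Inputs from Section 6.4: 20% in usual care, a 5-point difference, alpha 0.05, power 0.80, about 1,100 per arm. Sidedness is not stated; two-sided reproduces the figure. With mean proportion 0.225:

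n = [1.96·√(2 × 0.225 × 0.775) + 0.8416·√(0.20 × 0.80 + 0.25 × 0.75)]² / 0.05² = (1.1575 + 0.4961)² / 0.0025 ≈ 1,094.

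Power at 1,100 per arm = Φ[(0.05 − 1.96 × 0.01781) / 0.01777] = 0.802. The stated figure reproduces and is not in error.

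**3. Effect of doses between message and visit.** The documents give no rate, so let *e* be an assumed excess in a message arm. Assume true uptake from message through visit is 25% versus 20%, with no such doses in usual care. The message-arm rate becomes

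- excluded: (0.25 − e)/(1 − e), with the arm reduced to n(1 − e);
- kept and counted as not boosted at the visit: 0.25 − e.

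Sections 4.2 and 6.4 expect 5,000 patients or more, and 5,000/3 is about 1,666 per arm, so both sizes are shown.

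| e (points) | Excluded: rate, difference | Power at 1,100 / 1,666 | Counted as not boosted: rate, difference | Power at 1,100 / 1,666 |
|---|---|---|---|---|
| 0 | 25.0%, 5.0 | 0.80 / 0.93 | 25.0%, 5.0 | 0.80 / 0.93 |
| 0.5 | 24.6%, 4.6 | 0.74 / 0.89 | 24.5%, 4.5 | 0.72 / 0.88 |
| 1 | 24.2%, 4.2 | 0.67 / 0.84 | 24.0%, 4.0 | 0.62 / 0.80 |
| 2 | 23.5%, 3.5 | 0.50 / 0.68 | 23.0%, 3.0 | 0.40 / 0.56 |

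Both treatments understate the effect on uptake through the visit. Against a strict at-visit endpoint, exclusion works slightly the other way (24.2% rather than 24.0% at e = 1), because it shrinks the denominator.

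**4. No excess.** If 0.5 to 1 point is boosted before the visit in every arm and excluded, the rates are (0.25 − 0.005)/0.995 = 24.6% versus (0.20 − 0.005)/0.995 = 19.6%, or 24.2% versus 19.2%. The difference stays at 5.0 to 5.1 points and power at 0.81 to 0.82. Only an excess over usual care matters.

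**5. Secondary endpoint.** Section 6.4 gives 25% in usual care. Assuming 30% with a message, power at 1,100 per arm is 0.75. If e = 2 points is lost, the message rate is 0.28/0.98 = 28.6% when excluded (difference 3.6, power 0.47) or 28.0% when not counted (difference 3.0, power 0.36). This applies only if the window opens at or after the visit. If it means cumulative status at 6 weeks, nothing is lost provided the patients are kept.

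All power figures treat patients as independent, as Section 6.4 does. Assignment by visit day is a separate matter.

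**The case against.** The strongest reply is that Section 3 describes a look-ahead screen. It concerns identifying patients before an upcoming visit. Section 4.3 speaks of patients already eligible 2-3 days ahead, Section 4.1 gives the same order, and the schedule of activities puts identification under screening, before randomization. The registry check follows as part of identification, and nothing describes re-screening at the visit. This stands: exclusion is one reading and is not established.

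Several stronger inferences are tempting, and the documents do not support them.

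- *Section 5.6 shows that earlier doses are lost.* It reads as the timing of data capture and gives registry lag as its reason. As an event window it would conflict with an endpoint measured at the visit itself. Section 4.1 says the registry records when and where each dose was given, so a look-back is possible.
- *The 6-week endpoint certainly misses these doses.* Sections 2 and 5.2 say within 6 weeks of the visit, and Section 6.5.2 can be read as cumulative status.
- *The lost doses are message responders.* Usual-care patients can also be boosted in those days.
- *The how arm is penalised more than the why arm.* Section 5.2.1 says how messages also cover preparing for the visit, which points patients towards it.
- *The primary endpoint misclassifies early doses.* It is stated consistently as at the visit. That is a choice of what to measure, and widening it is a trade-off.

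The size is also open to challenge. An excess of 2 points would mean 40% of the planned effect (2/5) arising before the visit, among patients already booked. The 20% in Section 6.4 appears to be the at-visit rate, since a separate 25% is given for 6 weeks, so subtracting from the 5 points partly redefines the sponsor's assumption.

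What survives is that the literal text of Section 3 permits a post-assignment exclusion, nothing elsewhere forbids it, and the secondary window has two wordings.

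**Conclusion.** The concern holds as a defect of wording with a potentially serious consequence under one reading. Section 3 should be corrected so that it cannot be applied after assignment, and the secondary window needs one definition.

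The amount of bias cannot be derived from the documents. It is essentially zero if pre-visit boosting is equal across arms. If a message arm has an excess of 0.5 to 2 points that is excluded, the observed difference falls from 5.0 to between 4.6 and 3.5 points and power at 1,100 per arm from 0.80 to between 0.74 and 0.50. At about 1,666 per arm the corresponding range is 0.89 to 0.68. These figures rest on an assumed excess, no pre-visit boosting in usual care, and independent patients. Over 2-3 days the true excess may be small. The case for correction rests on protecting the comparison as assigned rather than on these figures.

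**What to change.** - **Section 3:** set booster-free status, and the registry check, at the identification date, before any message is sent and identically in all three arms. State that no assigned patient is removed from the analysis for a booster received later.
- **Sections 5.2 and 6.5.2** (and the matching line in Section 2): define the secondary endpoint as any booster, at any location, from identification through 6 weeks after the scheduled visit date. Section 5.6 ends collection 1 month after the visit, and that must be reconciled with a 6-week window.
- **Primary endpoint:** keep it at the targeted visit, with early-boosted patients in the denominator. Add a sensitivity analysis counting any booster from identification through the visit date.

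The cost is protocol and analysis-plan wording, since the registry already holds dose dates and places. Background boosters from those 2-3 days will enter the secondary count in all arms. The change does not restore power on the strict at-visit endpoint if messages do prompt early boosting; the sensitivity analysis and the secondary endpoint would show that effect.

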4. SUBJECT ENROLLMENT

4.1 Methods of enrollment

We will use the Mass General Brigham COVID-19 Vaccine Registry and Research Patient Data Registry (RPDR) and/or Epic Enterprise Data Warehouse (EDW) to identify eligible patients. The COVID-19 Vaccine Registry contains identified patient data, including the type of vaccine administered, first or second dose, as well as when and where the patient received their vaccine. The registry integrates information from vaccines administered by MGB, administrations entered into Epic based on patient report, and the state's Massachusetts Immunization Information System (MIIS) that includes vaccination sites across the state. General patient demographic information, adverse reactions and patient identifiers are included in the COVID-19 Vaccine Registry.

We will thus use the Mass General Brigham COVID-19 Vaccine Registry and EHR information in the Research Patient Data Registry (RPDR) and/or Epic Enterprise Data Warehouse (EDW) to identify MGB patients age ≥ 18 with an upcoming primary care outpatient appointment who are also eligible for the COVID booster vaccine based on routinely-collected data from these sources. We plan to launch the study after the booster vaccine has become widely available to adults and supply of vaccines at MGB is anticipated to be sufficient. Because the intervention cost is extremely low per patient, we plan to include all eligible patients.

4.2 Informed consent

As with other minimal-risk studies we have performed where informed consent is impracticable, we are requesting a waiver of informed consent and HIPAA authorization. There are several reasons for this. One, the nature of this communication-oriented intervention involves testing different messaging types utilizing secure communication channels that are already in use in routine clinical care. Second, the ability to understand the true effect of the intervention as it is delivered in the real world would be impossible to ascertain if formal informed consent from patients were sought. Third, obtaining formal informed consent would likely reduce the number of patients participating in the study, especially those from under-represented populations, and therefore undermine the generalizability of the study results, a foundational aspect of pragmatic clinical trial principles. Fourth, it would be extremely impractical as we expect more than 5,000 patients to still be eligible at the time of study launch. Fifth, contacting them in advance would actually introduce a co-intervention and reduce the ability to interpret the study findings. Finally, we will launch this project with approval by appropriate clinical leadership.

